#### **9.2.2.1 Electronic or Paper Diary Compliance**

Participant compliance with e-diary or paper diary solicited adverse event entry is not summarized.

#### **9.2.3 Unsolicited Adverse Events from Day 1 through Day 29**

All unsolicited AEs occurring during the specified collection period in the study are recorded, regardless of their assessment of relatedness by the investigator. Unsolicited AEs include also those solicited AEs ongoing after seven days post-injection (Day 8), AESI, and SAEs.

All reported unsolicited AEs are summarized by treatment group according to MedDRA SOC, PT and highest reported severity. When an unsolicited AE occurs more than once for a participant, the maximum severity and closest relationship to treatment is counted. The unsolicited AE analysis includes unsolicited AEs judged by the investigator as at least possibly related to IP.

### **9.3 Deaths, Other Serious Adverse Events and Other Significant Adverse Events**

#### **9.3.1 Deaths from Day 1 to Day 183 End of Study Visit**

Deaths are not expected in this study with healthy participants. A tabulation and participant data listing of AEs leading to death are provided.

#### **9.3.2 Serious Adverse Events from Day 1 to Day 183 End of Study Visit**

SAEs are tabulated by treatment group according to MedDRA SOC, PT and highest reported severity for both age groups and by age group stratum. A separate tabulation is limited to treatment-related SAEs only. A participant data listing of all SAEs is provided.

### **9.3.3 Adverse Event of Special Interest from Day 1 to Day 183 End of Study Visit**

AESI (see definition in Section 6.3) are tabulated by treatment group according to MedDRA SOC, PT and highest reported severity. In addition, solicited and unsolicited AESI are tabulated together.

### **9.3.4 Medically Attended Adverse Events from Day 1 to Day 183 End of Study Visit**

MAAEs (see definition in Section 6.3) are tabulated by treatment group according to MedDRA SOC, PT and highest reported severity for both age groups and by age group stratum.

### **9.3.5 Adverse Events Leading to Study Discontinuation from Day 1 to Day 183 End of Study Visit**

A participant data listing of all AEs leading to study discontinuation (see definition in Section 6.3) is provided.

### **9.3.6 Day 1 Adverse Events**

A participant data listing of all AEs occurring post-vaccination on Day 1 is generated.

## **9.4 Clinical Laboratory Tests**

Not applicable.

### **9.4.1 Pregnancy Testing**

Not applicable.

### **9.4.2 Viral Serology Testing at Screening**

Viral serology testing results are supplied in a participant listing.

## **9.5 Vital Signs, Physical Findings and Other Variables Related to Safety**

### **9.5.1 Vital Signs**

Observed values in vital signs include temperature, blood pressure, respiratory rate, and heart rate at the screening visit and pre- and post-vaccination on Day 1. All vital sign records are displayed in the participant data listings.

### **9.5.2 Physical Examinations**

Physical examinations by body system include a complete examination at screening and directed examinations at Days 1, 15, 22 and 183 only if indicated in order to determine if an AE needs to be recorded. Physical examination findings are listed by participant.

## **10 DATA MONITORING AND INTERIM ANALYSIS**

### **10.1 Safety Monitoring Committee**

The SMC reviews aggregated, blinded safety data after the first 50 participants have completed at least seven days of safety follow-up and periodically thereafter as per SMC recommendation according to the SMC Charter.

### **10.2 Interim Analysis**

#### **10.2.1 Preliminary Safety and Immunogenicity Analysis after Day 29 Visit**

After required data entry and cleaning has been completed, there is a preliminary analysis of safety and immunogenicity on data for all participants through the Day 29 Visit to facilitate health authority presubmission preparation. The analyses are performed by an unblinded third-party vendor and results are reported to the Sponsor only at the treatment group summary level, preserving the double-blind status on the participant level. No p-value penalty is assessed because the Day 22 primary immunogenicity endpoint data are final at the time of preliminary analysis and no action regarding the study is made based on these findings. The Sponsor, participants, and site personnel are not unblinded at the participant level until all follow-up visits are completed for the study through Day 183 EOS.

## APPENDIX I LIST OF TABLES, FIGURES, AND LISTINGS

Note the list of TFLs is a living document and subject to changes during the study.

Table	Title
Baseline	
14.1.1	Participant Enrollment by Site – Randomized Population
14.1.2	Analysis Populations – All Participants
14.1.3	Participant Disposition – Randomized Population
14.1.4.1	Demography – Randomized Population, Both Ages Pooled and by Age Group
14.1.4.2	Demography – Safety Population, Both Ages Pooled and by Age Group
14.1.4.3	Demography – Modified Intent-to-treat Population, Both Ages Pooled and by Age Group
14.1.4.4	Demography – Immunogenicity Evaluable Population, Both Ages Pooled and by Age Group
14.1.5	Medical History – Randomized Population
14.1.6	Timing of Blood Sample Collection – Randomized Population
14.1.7.1	Important Protocol Deviations – Randomized Population
14.1.7.2	Reasons for Exclusion from Analysis Populations – Randomized Population
14.1.8.1	Prior and Concomitant Medications by Descending Frequency within ATC Class and Drug Name – Safety Population
14.1.8.2	Concomitant Vaccines by Descending Frequency within ATC Class and Drug Name – Safety Population
Immunogenicity	
14.2.1.1.1	Anti-CHIKV SNA Seroresponse Rate by Treatment Group and Visit – Immunogenicity Evaluable Population, Both Ages Pooled and by Age Group
14.2.1.1.2	Anti-CHIKV SNA Seroresponse Rate by Treatment Group and Visit – Immunogenicity Evaluable Population, Both Ages Pooled by Sex Subgroups
14.2.1.1.3	Anti-CHIKV SNA Seroresponse Rate by Treatment Group and Visit – Immunogenicity Evaluable Population, Both Ages Pooled by Race Subgroups
14.2.1.1.4	Anti-CHIKV SNA Seroresponse Rate by Treatment Group and Visit – Immunogenicity Evaluable Population, Both Ages Pooled by Ethnicity Subgroups
14.2.1.1.5	Anti-CHIKV SNA Seroresponse Rate by Treatment Group and Visit – Immunogenicity Evaluable Population, Both Ages Pooled by Baseline Serostatus Subgroups
	Note: Only needed if baseline seropositive rate is <math>\geq 10\%</math>.
14.2.1.2.1	Anti-CHIKV SNA Seroresponse Rate by Treatment Group and Visit – mITT Population, Both Ages Pooled and by Age Group
14.2.1.2.2	Anti-CHIKV SNA Seroresponse Rate by Treatment Group and Visit, Sensitivity Analyses – mITT Population, Both Ages Pooled and by Age Group
14.2.2.1.1	Anti-CHIKV SNA GMT by Treatment Group and Visit – Immunogenicity Evaluable Population, Both Ages Pooled and by Age Group
14.2.2.1.2	Anti-CHIKV SNA GMT by Treatment Group and Visit – Immunogenicity Evaluable Population, Both Ages Pooled by Sex Subgroups
14.2.2.1.3	Anti-CHIKV SNA GMT by Treatment Group and Visit – Immunogenicity Evaluable Population, Both Ages Pooled by Race Subgroups
14.2.2.1.4	Anti-CHIKV SNA GMT by Treatment Group and Visit – Immunogenicity Evaluable Population, Both Ages Pooled by Ethnicity Subgroups

Table	Title
14.2.2.1.5	Anti-CHIKV SNA GMT by Treatment Group and Visit – Immunogenicity Evaluable Population, Both Ages Pooled by Baseline Serostatus Subgroups Note: Only needed if baseline seropositive rate is <math>\geq 10\%</math>.
14.2.2.2.1	Anti-CHIKV SNA GMT by Treatment Group by Visit – mITT Population, Both Ages Pooled and by Age Group
14.2.2.2.2	Anti-CHIKV SNA GMT by Treatment Group and Visit, Sensitivity Analyses – mITT Population, Both Ages Pooled and by Age Group
14.2.3	Geometric Mean Fold Increase from Baseline in Anti-CHIKV SNA Titer from Day 1 to each Visit by Treatment Group – Immunogenicity Evaluable Population, Both Ages Pooled and by Age Group
14.2.4	Participants with Anti-CHIKV SNA at or Above Selected Titers by Treatment Group and Visit – Immunogenicity Evaluable Population, Both Ages Pooled and by Age Group
Safety	
14.3.1	Vaccine Administration – Randomized Population
14.3.2.1	High Level Summary of Solicited and Unsolicited Adverse Events – Safety Population, Both Ages Pooled
14.3.2.2.1	Solicited Adverse Events by Highest Reported Severity – Safety Population, Both Ages Pooled and by Age Group
14.3.2.2.2	Solicited Adverse Events by Highest Reported Severity – Safety Population, Both Ages Pooled by Sex Subgroups
14.3.2.2.3	Solicited Adverse Events by Highest Reported Severity – Safety Population, Both Ages Pooled by Race Subgroups
14.3.2.2.4	Solicited Adverse Events by Highest Reported Severity – Safety Population, Both Ages Pooled by Ethnicity Subgroups
14.3.2.3	Solicited Events of Severe (Grade 3) or Higher Severity by Highest Reported Severity – Safety Population, Both Ages Pooled
14.3.2.4	Treatment-related Solicited Adverse Events by Highest Reported Severity – Safety Population, Both Ages Pooled
14.3.2.5.1	Day of Onset for Participants who Reported Solicited Adverse Events – Safety Population, Both Ages Pooled
14.3.2.5.2	Day of Onset for Participants who Reported Treatment-related Solicited Adverse Events – Safety Population, Both Ages Pooled
14.3.2.6.1	Number of Days with Symptoms for Participants who Reported Solicited Adverse Events – Safety Population, Both Ages Pooled
14.3.2.6.2	Number of Days with Symptoms for Participants who Reported Treatment-related Solicited Adverse Events – Safety Population, Both Ages Pooled
14.3.2.7	Percentage of Participants with Solicited Adverse Events by Day on Study – Safety Population, Both Ages Pooled
14.3.3.1	Solicited and Unsolicited Adverse Events by System Organ Class, Preferred Term and Highest Reported Severity – Safety Population, Both Ages Pooled and by Age Group
14.3.3.2	Solicited and Unsolicited Adverse Events by Highest Reported Severity – Safety Population by Sex Subgroups
14.3.3.3	Solicited and Unsolicited Adverse Events by Highest Reported Severity – Safety Population by Race Subgroups
14.3.3.4	Solicited and Unsolicited Adverse Events by Highest Reported Severity – Safety Population by Ethnicity Subgroups

Table	Title
14.3.3.5	Solicited and Unsolicited Adverse Events Excluding Serious Adverse Events by System Organ Class, Preferred Term and Highest Reported Severity – Safety Population, Both Ages Pooled
14.3.4.1	Listing of Serious Adverse Events – Safety Population, Both Ages Pooled
14.3.4.2	Listing of Adverse Events Leading to Study Discontinuation – Safety Population, Both Ages Pooled
14.3.4.3	Listing of Adverse Events Leading to Death – Safety Population, Both Ages Pooled
14.3.5.1	Unsolicited Adverse Events in Descending Frequency by Preferred Term – Safety Population, Both Ages Pooled
14.3.5.2	Unsolicited Adverse Events by System Organ Class, Preferred Term and Highest Reported Severity – Safety Population, Both Ages Pooled and by Age Group
14.3.5.3	Unsolicited Adverse Events of Severe (Grade 3) or Higher Severity in Descending Frequency by Preferred Term – Safety Population, Both Ages Pooled
14.3.5.4	Unsolicited Adverse Events of Severe (Grade 3) or Higher Severity by System Organ Class, Preferred Term and Highest Reported Severity – Safety Population, Both Ages Pooled
14.3.5.5	Treatment-related Unsolicited Adverse Events in Descending Frequency by Preferred Term – Safety Population, Both Ages Pooled
14.3.5.6	Treatment-related Unsolicited Adverse Events by System Organ Class, Preferred Term and Highest Reported Severity – Safety Population, Both Ages Pooled
14.3.5.7	Serious Adverse Events by System Organ Class, Preferred Term and Highest Reported Severity – Safety Population, Both Ages Pooled and by Age Group
14.3.5.8	Treatment-related Serious Adverse Events by System Organ Class, Preferred Term and Highest Reported Severity – Safety Population, Both Ages Pooled
14.3.5.9	Adverse Events of Special Interest by System Organ Class, Preferred Term and Highest Reported Severity – Safety Population, Both Ages Pooled
14.3.5.10	Adverse Events of Special Interest Including Solicited Events by System Organ Class, Preferred Term and Highest Reported Severity – Safety Population, Both Ages Pooled
14.3.5.11	Medically Attended Adverse Events by System Organ Class, Preferred Term and Highest Reported Severity – Safety Population, Both Ages Pooled and by Age Group
14.3.5.12	Treatment-related Medically Attended Adverse Events by System Organ Class, Preferred Term and Highest Reported Severity – Safety Population, Both Ages Pooled

Figure	Title
14.4.2.1.1	Forest Plot of Seroresponse Rate at Day 22 – Immunogenicity Evaluable Population, Both Ages Pooled and by Age Group
14.4.2.1.2	Forest Plot of Seroresponse Rate at Day 22 – Immunogenicity Evaluable Population, Both Ages Pooled by Sex, Race, and Ethnicity Subgroups
14.4.2.2.1	Geometric Mean Anti-CHIKV SNA Titers by Visit – Immunogenicity Evaluable Population, Both Ages Pooled
14.4.2.2.2	Reverse Cumulative Distribution of Anti-CHIKV SNA Titers by Visit – Immunogenicity Evaluable Population, Both Ages Pooled
14.4.2.3.1	Geometric Mean Fold Increase in Anti-CHIKV SNA Titers by Visit – Immunogenicity Evaluable Population, Both Ages Pooled

Figure	Title
14.4.2.3.2	Reverse Cumulative Distribution of Geometric Mean Fold Increase in Anti-CHIKV SNA Titers by Visit – Immunogenicity Evaluable Population, Both Ages Pooled

Listing	Title
16.1.6 and	
16.1.7	Participant Randomization Assignments
16.2.1.1	Participant Disposition
16.2.1.2	Reasons for Screen Failure
16.2.2.1	Participants Randomized who Did Not Satisfy Entry Criteria
16.2.2.2	Participants who Received the Wrong Treatment or an Incorrect Dose
16.2.2.3	Participants who Received an Excluded Concomitant Medication or Vaccine
16.2.2.4	Important Protocol Deviations
16.2.3	Analysis Populations
16.2.4.1	Demography
16.2.4.2.1	Medical History
16.2.4.2.2	Verbatim to Preferred Term Mapping for Medical History
16.2.4.3	Prior and Concomitant Medications and Vaccines
16.2.4.4	Verbatim to Preferred Name Mapping for Concomitant Medications
16.2.5	Anti-CHIKV SNA Titers
16.2.6	Study Vaccine Administration
16.2.7.1	Solicited Adverse Events
16.2.7.2.1	Unsolicited Adverse Events
16.2.7.2.2	Unsolicited Adverse Events Occurring Postvaccination on Day 1
16.2.7.3	Verbatim to Preferred Term Mapping for Unsolicited Adverse Events
16.2.7.4	Participant Identification of Adverse Events
16.2.8.1	Vital Sign Results
16.2.8.2	Physical Examination Results
16.2.8.3	Viral Screening Results
16.2.8.4	Hospitalization Details
16.2.8.5	Death Details

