## 5.3 Analysis Populations

Analyses are based on the following study populations:

**Randomized Population:** All screened participants who provide informed consent and provide demographic and other screening measurements and are randomized (i.e., have a randomization number assigned within the EDC system). Most baseline summaries and the IP administration summary use the randomized population.

**Exposed Population:** All participants in the randomized population who receive IP.

**Safety Population:** All participants in the exposed population who provide safety assessment data. This generally includes any participant who was not lost to follow-up at Day 1 (baseline), as they are at risk for reporting an SAE. Participants are analyzed as treated (i.e., according to the treatment a participant received, rather than the treatment to which the participant was randomized). All safety analyses use the safety population.

**Modified Intent-to-Treat (mITT) Population:** All randomized participants who are vaccinated and have at least one post-injection anti-CHIKV human SNA assay result. Participants are counted in the group to which they were randomized. Primary and secondary immunogenicity analyses are repeated for the mITT population as a measure of robustness of the results.

**Immunogenicity Evaluable Population (IEP):** The IEP includes all participants in the mITT population who:

- Provide evaluable serum sample results for the relevant post-vaccination time points, and within the required time frames:
  - Day 22: Day 19 through Day 27, inclusive.
- Have no measurable ( $\geq$ LLOQ) anti-CHIKV human SNA assay titer at Day 1 (baseline), i.e., seronegative at baseline. Note that participants with missing Day 1 (baseline) are excluded from IEP.
- Have no important protocol deviation deemed exclusionary or other reason to be excluded as defined prior to unblinding.

The IEP is the primary population for all immunogenicity analyses.

**CHIKV Genotype Subset:** The CHIKV genotype subset includes those IEP participants who received PXVX0317 and are selected for genotype analysis. See Section 8.4.3 for details.

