**Baseline seropositive rate** is defined as the percentage of participants with anti-CHIKV human SNA assay titer  $\geq$ LLOQ prior to IP administration.

**Body mass index** at screening visit is automatically calculated by EDC as a participant's weight in kg divided by height in  $\text{m}^2$ .

**Anti-chikungunya virus (anti-CHIKV) human SNA assay NT80 (80% neutralizing titer)** is defined as the dilution factor that corresponds to an 80% reduction of luciferase activity compared to virus-only control. Anti-CHIKV SNA titer values below LLOQ are replaced by LLOQ/2 in the immunogenicity analyses including GMT and GMFI. For the 4-fold rise over Day 1 (baseline), values below the LLOQ are replaced with the LLOQ.

**Completion of study** for an individual participant is defined as completion of the Day 183 EOS and any required safety follow-up (i.e., a disposition status of completed).

**Early discontinuation** for an individual participant is defined as completion of the Early Discontinuation/ Withdrawal Visit (i.e., a disposition status other than completed).

**Enrolled/randomized** is defined as receipt of a randomization number assignment within the EDC system.

**Medical history** items entered on the medical history eCRF are considered to predate the study regardless of onset date.

**Medication, concomitant**, is defined as one taken after start of IP administration on Day 1 (baseline) through the end of study. For analysis purposes, any medication which is ongoing or with a stop date that is on or after the start date of IP administration is categorized as a concomitant medication. Partial or missing concomitant medication start and/or end date are imputed according to Section [6.5.2](#).

**Medication, prior**, is defined as one with a stop date within 30 days prior to the screening visit (90 days for blood products) through the start of IP administration on Day 1 (baseline).

**Protocol deviations** are defined by inclusion in the EDC protocol deviation module (participant-level only, not site-level), including monitor-identified deviations as well as Sponsor- and EDC system-identified programmatic deviations. Protocol deviations are classified by category and type (important/not important).

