**Randomized participant not meeting entry criteria** is defined using the protocol deviation dataset and not just the inclusion exclusion criteria dataset, because a project team decision was made to keep the inclusion exclusion criteria as entered at the time of randomization even if the participant was later found to have violated entry criteria. These violations are recorded as protocol deviations.

**Rounding of values** is described in Section 6.2.

**Seroresponse rate** is defined as the percentage of participants who achieve an anti-CHIKV SNA titer █.

**Study Day 1** is defined as the day of IP administration on Day 1 (baseline). The day prior to Day 1 is Day -1. There is no Day 0. If the participant is not treated, then the Day 1 (baseline) is defined as the day of randomization.

Study day relative to Day 1 are calculated as:

- **Study Day** = (assessment date – date of Day 1 + 1) if the assessment is on or after Day 1.
- **Study Day** = (assessment date – date of Day 1) if the assessment is before Day 1.

For conversion of durations, 1 year = 365.25 days and 1 month = 365.25/12 = 30.4375 days.

**Subgroups** for sex (male and female), race (white and non-white) and ethnicity (Hispanic or Latino and Not Hispanic or Latino) are defined based on the corresponding demographic questions. Participants missing sex, race or ethnicity will be omitted from analyses by subgroup. Participants with “Not Reported” or Unknown” ethnicity are not included in ethnicity subgroups.

**Summary statistics** are described in Section 6.1.

**Time duration (in days) between event A and event B** is (date of event B – date of event A + 1). For conversion of durations, 1 year = 365.25 days and 1 month = 365.25/12 = 30.4375 days.

**Treatment, actual**, is defined as the treatment administered to the participant by the site (i.e., corresponding to the kit number used).

**Treatment group** is defined as PXVX0317 vaccine vs. placebo.

**Treatment, randomized**, is defined as the treatment assigned to the participant by the EDC (i.e., corresponding to the kit number assigned).

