### 6.5.3 Missing Outcome and Covariates

Participants are included in the analyses to the extent of their available data; missing immunogenicity data are not imputed. See Sections 5.5 and 5.7 and definition of anti-CHIKV human SNA assay titer in Section 6.3.

Participants with missing categorical data are counted in missing or unknown categories when appropriate. Participants with missing numeric data are treated as missing completely at random when calculating summary statistics. For likelihood-based analyses (e.g., regression), missing at random is assumed.

As sensitivity analyses for the coprimary endpoints (difference in anti-CHIKV SNA seroresponse rate between PXVX0317 and placebo at Day 22 and GMTs at Day 22), missing immunogenicity outcome data at Day 22 are imputed conservatively as described below. Participants who have an out-of-window result at Day 22 (before Day 19 or after Day 27), are seropositive at baseline, or have an exclusionary PD are included in the mITT population but not the IEP population for these sensitivity analyses.

- Nonresponder analysis. Participants' missing Day 22 anti-CHIKV SNA titer value is imputed as the assay LLOQ/2, even for participants in the PXVX0317-vaccinated group.
- Last observation carried forward (LOCF) analysis. Participants' Day 15 immunogenicity value is substituted for the missing Day 22 anti-CHIKV SNA titer value.

The endpoints are recalculated using each method of conservative imputation and reported for the mITT population to assess the robustness of primary endpoint results to informative missingness.

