## 6.8 Subgroup Analyses

Summaries pool both age groups and are repeated separately for each age group. Analyses of the primary immunogenicity and safety endpoints are also summarized by sex, race, and ethnicity group along with treatment group. Summaries by baseline anti-CHIKV SNA serostatus are reported if the baseline (Day 1) seropositive rate is  $\geq 10\%$ .

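### SAP Appendix I splits the seronegative-only IEP by baseline serostatus, so Tables 14.2.1.1.5 and 14.2.2.1.5 cannot show the seropositive results that SAP 8.4 promises

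*SAP*

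**What the plan says.** **The tables.** SAP Appendix I lists Tables 14.2.1.1.5 (seroresponse rate) and 14.2.2.1.5 (GMT). Both titles name the same population and split: "Immunogenicity Evaluable Population, Both Ages Pooled by Baseline Serostatus Subgroups". A note under each says it is needed only if the baseline seropositive rate is at least 10%. The appendix opens with a caveat: "Note the list of TFLs is a living document and subject to changes during the study".

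**The population.** SAP 5.3 requires IEP members to have no measurable "titer at Day 1 (baseline), i.e., seronegative at baseline", and excludes anyone with no Day 1 result. Protocol 9.2 has the same seronegativity criterion. SAP 5.3 adds: "The IEP is the primary population for all immunogenicity analyses". The mITT, by contrast, takes randomized and vaccinated participants with one or more post-injection titers, with no condition on serostatus.

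**The trigger.** SAP 6.3 says that the baseline seropositive rate "is defined as the percentage of participants with anti-CHIKV human SNA assay titer" at or above the LLOQ before dosing. SAP 6.8 states: "Summaries by baseline anti-CHIKV SNA serostatus are reported if the baseline (Day 1) seropositive rate is" 10% or higher. Protocol 9.6.5 sets the condition at more than 10% and makes the analysis optional. None of these places names an analysis population for the rate.

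**The promise.** SAP 8.4 commits to serostatus subgroup analyses, positive and negative, of the coprimary endpoints and the key secondary seroresponse endpoints once the trigger is met. That sentence names no population. The sentence before it, on sex, race and ethnicity, names the IEP.

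**The concern.** A split by baseline serostatus has a purpose only if both groups can contain participants. Here the population named in the titles removes one of the two groups by definition. A programmer who follows the list would produce two tables that omit the result they exist to report.

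The body of the SAP does not redirect the programmer. SAP 5.3 makes the IEP the default for immunogenicity, and the neighboring subgroup sentence in SAP 8.4 uses the IEP. SAP 8.4.1.1 and 8.4.1.2 also leave subgroups out of the mITT repeats. At stake is a prespecified summary, by arm, of how participants with existing antibody respond. If the omission is found only after unblinding, the population for that summary would be chosen with results in hand.

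**Working it through.** **1. Set logic (no data needed).**

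| Source | Rule |
|---|---|
| SAP 6.3 | Seropositive = Day 1 titer at or above LLOQ |
| SAP 5.3, IEP | Day 1 titer present and below LLOQ |
| SAP 5.3, mITT | No serostatus condition |
| Appendix I, 14.2.1.1.5 and 14.2.2.1.5 | IEP, split by serostatus |

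Seropositives in the IEP = 0. The seronegative column is therefore the whole IEP. With the same participants and the same methods, it reproduces the pooled-age results of Tables 14.2.1.1.1 and 14.2.2.1.1.

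**2. Other listed outputs.** Appendix I has no mITT table by serostatus. The mITT tables (14.2.1.2.1, 14.2.2.2.1 and the sensitivity tables) mix both serostatus groups. Table 14.1.4.3 gives mITT serostatus counts, and Listing 16.2.5 gives individual titers. Neither summarizes the seropositive response by arm.

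**3. The plan's own size figure.** Inputs are 200 per arm (SAP 2.2) and 10% non-evaluable (SAP 4.1). 200 × (1 − 0.10) = 180 per arm, which matches SAP 4.1. In total, 2 × 180 = 360 are evaluable and 400 − 360 = 40 are not.

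**4. Can the trigger be met under that assumption?** Every seropositive participant is outside the IEP, so at most 40 can be seropositive.

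- Denominator of all randomized: maximum = 40/400 = 10.0%.
- Denominator of the mITT: let x of the 40 have no post-injection titer (x is assumed). Maximum share = (40 − x)/(400 − x).

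| x | Maximum seropositive share of mITT |
|---|---|
| 0 | 40/400 = 10.0% |
| 10 | 30/390 = 7.7% |
| 20 | 20/380 = 5.3% |

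On the mITT, the SAP trigger is met only if all 40 are seropositive and x = 0. On all randomized, it is met only if all 40 are seropositive. On either denominator the protocol's stricter condition is not met, because the maximum is exactly 10.0%.

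**5. Does the denominator matter?** Only near the cut-off. As an illustration, 39 seropositives are 39/400 = 9.75% of all randomized but 39/390 = 10.0% of an assumed mITT of 390. That case has 39 + 10 = 49 non-evaluable participants, above the planned 40. The two inequalities differ only at exactly 10%, for example 40/400.

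**The case against.** The strongest reply is that this is a table-title slip in a list declared open to change. An empty column would be noticed at programming and would mislead nobody. The analysis is conditional and descriptive, and the protocol makes it optional. SAP 1 also mentions table shells with programmer's notes, which may name the right population. They were not available for this review, so the finding is limited to the SAP text and its Appendix I list.

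Much of this stands, and it is why the point ranks low. It does not remove the point. The note about changes makes the titles easy to correct but supplies no other population, and SAP 8.4, which commits to the analysis, names none either.

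A reader might infer three stronger things that the documents do not support:

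- **That the trigger can never fire because the IEP rate is always 0%.** SAP 6.3 defines the rate over participants and does not restrict it to the IEP. The real gap is the choice among randomized, safety and mITT, which matters only close to 10%.
- **That seropositive data are lost.** They enter the mITT tables and Listing 16.2.5. Comparing IEP with mITT results separates them in part. Only the promised summary by arm is missing.
- **That the title error dilutes the mITT results.** Those tables are planned anyway and do not change with these titles.

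SAP 6.5.3 says that participants who "are seropositive at baseline, or have an exclusionary PD are included in the mITT population but not the IEP population", but that sentence is confined to the sensitivity analyses. The firmer ground for placing seropositives in the mITT is its definition in SAP 5.3.

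**Conclusion.** The point holds, at low severity. As written, the two tables cannot report a seropositive result, and nothing else listed does so. This follows from the definitions and rests on no assumption about the data.

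The practical effect is small. Under the planned 10% non-evaluable rate, the SAP trigger is reached only in the extreme case where all 40 non-evaluable participants are seropositive and, on an mITT denominator, all have a post-injection titer. That rate is a planning assumption and not a cap, so the contingency could still arise.

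It would be wrong to read this as a flaw in the primary analysis. The coprimary and key secondary tests use the IEP as defined, and they, alpha and power are unaffected.

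**What to change.** Before unblinding:

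1. Retitle Tables 14.2.1.1.5 and 14.2.2.1.5 to the mITT population.
2. Name the mITT in the serostatus sentence of SAP 8.4. In SAP 8.4.1.1 and 8.4.1.2, except baseline serostatus from the statement that mITT repeats exclude subgroups. This is required, because otherwise the new titles would contradict those sections.
3. In SAP 6.8, state the denominator of the trigger, for example mITT participants with a Day 1 titer, arms pooled.
4. Say how a missing Day 1 titer is handled in the serostatus tables. SAP 6.3 has an omission rule for other subgroups ("Participants missing sex, race or ethnicity will be omitted from analyses by subgroup"), while SAP 6.5.3 puts missing categorical values in a missing or unknown category where appropriate. The handling should be consistent with SAP 6.5.3.
5. Use one inequality. Taking the protocol's version into the SAP avoids a protocol amendment.

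**Cost.** Two table titles and short edits in SAP 6.8, 8.4, 8.4.1.1 and 8.4.1.2. No new analysis set, no new data, and no effect on alpha or sample size.

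**Downside.** The mITT seronegative column will also include participants with out-of-window Day 22 samples or exclusionary deviations, so it will not match the IEP results exactly. A footnote should say so.
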